H_{1a} will be tested by the significance of the [group x time] contrast from Baseline to POST-4wk for the 6-minute walk test at $\alpha=0.05$. For H_{1b}, secondary outcomes will be tested separately using the same model as H_{1a} to identify the most sensitive measures to carry forward into future studies.¹¹⁰ The Benjamini-Hochberg procedure²²³ will be used to control the false discovery rate (FDR) for the secondary outcomes.

Aim 2: Determine the minimum locomotor training duration needed to maximize immediate effects

Hypothesis 2a (H_{2a}): Within the HIT group, *walking capacity* (6 minute walk test distance) and *secondary outcomes* will significantly increase from 4WK to 8WK and from 8WK to 12WK

Hypothesis 2b (H_{2b}): Compared to MAT, HIT will elicit significantly greater improvements in *walking capacity* and *secondary outcomes* from PRE to 8WK and from PRE to 12WK

H_{2a} will be tested by the significance of the respective time contrasts within the HIT group. **H_{2b}** will be tested by the significance of the respective [group x time] contrasts. Secondary outcomes will have FDR control.²²³

Data and Safety Monitoring Plan

An adverse event (AE) is an undesired medical occurrence in a participant who is undergoing study procedures and does not necessarily have a causal relationship with the treatment or study procedures. This includes any adverse clinical change that occurs at any time following consent. A serious AE (SAE) is any adverse experience occurring during study participation that results in any of the following outcomes: death; a life threatening situation; inpatient hospitalization or prolongation of existing hospitalization; a persistent or significant disability/incapacity.^{209,210} The data and safety monitoring plan for this study will include participant monitoring for AEs and other problems, review of AEs and other problems by the study team and IRB, and an independent data safety monitoring board (DSMB).

Participant safety monitoring

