Based on safety data from our preliminary studies^{9,12} and the extensive previous HIT research among persons with heart disease,^{65,72,76,77,98-101} and MAT research among persons post-stroke,³³ we expect a similar rate of non-serious adverse events (AEs) between HIT and MAT (e.g. temporary exercise-related soreness and fatigue), without any study-related serious AEs. As in our previous studies, we will systematically monitor for AEs. Each study visit, participant voluntary reporting of AEs will be encouraged and AEs of interest will be specifically queried, including: falls, injuries, faintness, pain and fatigue. During training, safety monitoring will include HR, blood pressure, and continuous observation for other signs or symptoms of cardiorespiratory insufficiency, worsening neurologic impairments or orthopedic injury, using accepted stopping criteria.^{142,208} AEs will be followed until resolution and categorized according to type and severity (grade 1-5),^{209,210} causal relationship with the intervention (yes/possibly/no) and whether anticipated (listed in the protocol / informed consent form or expected in the target population).

Reporting and review of AEs and other problems involving risk

All observed or volunteered AEs and other problems involving risk to research participants or others that occur throughout the study will be recorded and reported to the IRB according to UC IRB protocol, as well as reported to the DSMB (see further information about the DSMB below).. As such, all *unanticipated* AEs and other problems involving risk will be reported to the IRB and DSMB within 10 days of study staff knowledge of the event. AEs or other problems resulting in temporary or permanent interruption of the study activities by the PI to avoid potential harm to participants will be reported to the IRB and DSMB immediately (within 48 hours). Other AEs or study problems will be reported to the IRB at the time of continuing review and to the DSMB at least annually. AEs will be discussed between site PIs during regular conference calls. Withdrawal from the study and modifications to study procedures as a result of an AE or because of therapeutic measures taken to treat an AE will be at the discretion of the site PIs, in consultation with the study physicians as appropriate.

Data safety monitoring board (DSMB)

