The DSMB will consist of at least 3 members separate from the study team, including at least one physician and at least one biostatistician, with collective experience in the management of patients with stroke, exercise and clinical trials. A quorum will require at least 2 members, including the chair. Persons with a significant conflict of interest (financial, institutional or scientific) will not be permitted to be DSMB members. The DSMB will meet at least (approximately) annually. A summary report will be sent to the DSMB prior to each meeting, including safety and clinical outcome data. DSMB meetings will include open sessions where the DSMB may discuss any issues with the study team and closed sessions where the DSMB alone decides on its recommendations. The DSMB will assess the risks and benefits of study participation for all participants and will provide a written report of their analyses and recommendation as to whether the study should continue, whether modifications to the study are needed or if the study should be terminated. These reports will be sent to the investigators and the IRB.

Safety Data Analysis

In the unexpected event of one or more SAEs, the SAE rate will be compared between groups to confirm that there is no significant difference in major safety risk between HIT and MAT. This analysis will use a logistic regression model with SAE (yes/no) as the dependent variable and fixed effects for group, site and baseline gait speed category. If there are SAE(s) in one group only, a continuity correction (0.5 SAEs added to each group) will still allow the odds ratio to be calculated.⁹ Secondary safety outcomes (different grades/categories of AEs) will be tested using the same model, with [# AEs / # training sessions] as the dependent variable.⁹

E.3. Data Storage and Confidentiality

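### DSMB reporting speed follows 'anticipated' status or a PI interruption, not seriousness or relatedness, so a related SAE of a listed type can, in a narrow case, wait for the annual report

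*Protocol*

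**What the plan says.** Protocol E.2, Data and Safety Monitoring Plan, defines seriousness by outcome: "A serious AE (SAE) is any adverse experience occurring during study participation that results in any of the following outcomes". The outcomes are death, threat to life, a new or prolonged inpatient stay, and lasting or significant disability. Under Participant safety monitoring, each AE is coded for type, for grade, and for "causal relationship with the intervention (yes/possibly/no"). A separate code records "whether anticipated (listed in the protocol / informed consent form or expected in the target population").

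The next subsection, on reporting and review of AEs, gives three routes to the DSMB:

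- **10 days.** This limit covers unanticipated events only: "AEs and other problems involving risk will be reported to the IRB and DSMB within 10 days of study staff knowledge of the event".
- **48 hours.** "AEs or other problems resulting in temporary or permanent interruption of the study activities by the PI to avoid potential harm to participants" are reported to the IRB and DSMB within this limit, anticipated or not.
- **Default.** "Other AEs or study problems will be reported to the IRB at the time of continuing review and to the DSMB at least annually".

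On meetings, the DSMB subsection says: "The DSMB will meet at least (approximately) annually". The SAP's Safety Data Analysis section compares SAE rates between groups and sets no reporting deadline.

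**The concern.** The DSMB is the independent body that recommends whether the trial continues, changes or stops. One would expect the seriousness of an event and its link to the intervention to decide how quickly the board hears of it. The protocol records both, and neither enters the reporting rule. The rule turns on whether the event was foreseen and on whether the PI chose to interrupt study activities.

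Foreseen is not the same as minor. In a trial of vigorous walking exercise after stroke, the gravest foreseeable events are cardiovascular, and these are easily coded as anticipated because the protocol names them. What is at stake is a delay in independent oversight of a related SAE. No estimand, test or error rate is affected.

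**Working it through.** The plan states no figure to reproduce. The check traces one event through the three routes and then measures the wait.

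**Test case.** A participant has a cardiovascular event that is related or possibly related to training and leads to hospital admission.

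1. *Is it serious?* Yes, by the E.2 definition. No route refers to that definition.
2. *Does the 10-day route apply?* Only if the event is unanticipated. Listing in the protocol is enough to make it anticipated, and G.1 Potential Risks lists cardiovascular events as a very low risk. The Background section also describes a high long-term risk of cardiac events in stroke survivors, which gives a second ground. The definition mentions neither grade, seriousness nor relatedness. The event can be coded anticipated, and this route then does not apply.
3. *Does the 48-hour route apply?* Only if the PI interrupts study activities to avoid harm. If sessions are missed simply because the participant is in hospital, it is unclear whether that is an interruption by the PI.
4. *Otherwise* the event is one of the other AEs. The DSMB hears at least annually, and the IRB at continuing review.

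**Length of the wait on the default route.** Assume reports every T days and an event equally likely on any day of the interval. Then the maximum wait is T, the mean is T/2, and the share of such events waiting more than 10 days is (T − 10)/T.

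| Report interval | Maximum | Mean | Share beyond 10 days |
|---|---|---|---|
| Annual, T = 365 | 365 days | 365/2 = 182.5 days | 355/365 = 0.973 |
| Six-monthly, T = 182.5 | 182.5 days | 182.5/2 = 91.25 days | 172.5/182.5 = 0.945 |

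The second row is included because annual is a minimum frequency and the sponsor may report more often.

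**Scale.** Protocol E.6 puts one person's participation at about 5 months, or 5 × 365/12 = 152 days, which is below the 182.5-day mean wait under annual reports. With even enrolment over the roughly 5-year study (an assumption), a 12-month interval takes in 50/5 = 10 to 75/5 = 15 new participants.

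All these figures are conditional on an SAE having reached the default route. The documents do not allow the probability of that to be estimated.

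**The case against.** **The 48-hour route may be wide.** Elsewhere the protocol uses the term study activities for one participant's procedures: in Screening and Baseline Assessment for a possible pregnancy, and in G.1 for blood glucose out of range. On that usage, pausing one person's training after a cardiac event would trigger 48-hour reporting, and such a pause is likely. This largely stands and removes much of the gap. What remains is that the route needs a decision by the PI, and nothing says outright that one participant's pause counts.

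**Related SAEs are not expected.** The plan anticipates similar rates of non-serious AEs "without any study-related serious AEs". Protocol Safety Data Analysis calls SAEs unexpected, and Emergency Response Planning in G.1 promises prompt reporting of AEs to the IRB and DSMB. Staff could well code a related SAE as unanticipated. This also stands as a likelihood. But the first two are statements of expectation, and the third gives no time limit and refers back to the same monitoring plan. The only written coding definition goes by listing or by expectation in the population.

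**Wording of the 10-day rule.** Its reference to other problems involving risk could be read to catch any serious event. AEs in that sentence are limited to unanticipated ones, however, and the remaining AEs then have their own annual route.

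**Unseen documents.** Reporting also follows the UC IRB protocol, and the consent form is separate. Either of these, or a DSMB charter, could set a stricter rule. This limits the point to the protocol and SAP.

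**Other protections.** ECG stress-test exclusions, in-session monitoring with stopping criteria, site-PI calls with study-physician input, and IRB review all remain. The team reports no SAE related to locomotor HIT in its own earlier studies.

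A reader might infer that the plan schedules SAEs for annual reporting, or that 97% of SAEs would be reported late. The documents support neither. Unanticipated or interrupting SAEs reach the DSMB in 10 days or 48 hours, and the percentage describes only the residual case. A reader might also infer that the DSMB cannot review an SAE before its annual meeting. In fact annual is a minimum, and a quorum of two members including the chair makes an early meeting practical.

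**Conclusion.** The point holds in a narrow form. As written, a related or possibly related SAE of a listed type can be coded anticipated and, if the PI does not interrupt study activities to avoid harm, can reach the DSMB as late as the next annual report. For such an event the wait is up to about 12 months, with a mean of about 6 months if reports are annual and events fall evenly over the year. With six-monthly reports the figures are about 6 and 3 months.

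How often this would occur is not estimated and is expected to be rare. The finding is a possible delay in independent oversight and gives no evidence of harm. The absence of a written event-triggered DSMB review is not a separate fault, since the protocol already allows more frequent meetings. The conclusion rests on the protocol and SAP alone. It is worth correcting because two defensible codings of the same event lead to deadlines of 10 days and about a year.

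**What to change.** In Protocol E.2, after the 48-hour rule, add a sentence to this effect: *Any SAE judged related or possibly related to the intervention or to study testing, anticipated or not, goes to the IRB and the DSMB no later than 10 days after study staff learn of it, or 48 hours if study activities are interrupted, including for a single participant.*

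Extend the causality code so that it asks about the intervention or study testing, keeping the answers yes, possibly and no. At present it asks about the intervention only, although AEs count from consent and participants undergo maximal exercise tests. Without this change the new sentence could not be applied to an SAE arising from a test. The promise of prompt reporting in G.1 would then point to a stated deadline.

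The cost is one sentence, one extended code and an occasional extra expedited report. The existing board and time limits are reused. The rule still depends on a staff judgement of relatedness, which the possibly category softens. A prompt unscheduled DSMB review after each such report is an optional addition.

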- The Stroke and Aphasia Quality of Life Scale,^{157,158} Stroke Impact Scale,¹³⁸ EQ-5D and Patient Health Questionnaire¹⁴⁷ are reliable and valid self-report quantitative surveys that include questions about quality of life. One or more of these questionnaires will be used.
- The Global Rating of Change (GROC)¹⁵⁹ is a questionnaire that assesses overall impressions of change in health status from the perspective of the participant. The GROC is a 15 point ordinal scale with -7 indicating "a very great deal worse," 0 indicating "no change," and +7 indicating "a very great deal better". The GROC is not applicable at baseline testing because it measures change only.

Heart rate data may also be recorded during the above testing. If there are any issues with data capture (e.g. equipment malfunction), it is possible that participants could be asked to repeat individual tests as long as it would still be possible to obtain quality data without increasing risk to the participant.

Randomization

Participants will be enrolled after PRE testing and randomized to either HIT or MAT. Randomization will be stratified by site and by baseline walking speed (<0.4 , ≥ 0.4 m/s), to help ensure that groups are balanced within sites and on this critical prognostic factor.^{149,150} Within each stratum, we will randomize in *block sizes of 2 or 4*. Block size will be *randomly permuted* to prevent personnel from being able to predict the last randomization within a block.

Training Intervention Protocols

Common features between protocols. Participants in both groups will be asked to perform 36 training sessions over approximately 12 weeks, with repeated outcome testing after each [12 session / 4 week] block. Target training frequency will be 3 sessions per week. Both groups will train for approximately 45 minutes per session, v.5, 16Mar2021

using orthotic & assistive devices and handrail balance support on the treadmill as needed.¹⁴⁴ Each session will include a 3 minute warm up, 10 min overground training with guarding from a physical therapist, 20 min treadmill training wearing a harness for fall protection, another 10 min overground training and a 2 min cool down. Target heart rates (HRs) will be based on the peak HR from exercise testing, to account for β -blocker medications.¹⁴⁴

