These risks will be minimized by: 1) recruiting a study sample with stable cardiovascular condition and normal cardiovascular responses to an exercise test (among other criteria);⁶ 2) using a screening and exercise testing protocol with a strong safety track record across >500 recorded exercise tests and well over 15,000 recorded treadmill aerobic exercise sessions among persons with stroke;^{33,144} 3) using HIT protocols that were developed and optimized by our research team in previous studies^{9,12} and in collaboration with a cardiologist. These protocols were also based on previous HIT studies among persons with heart disease that demonstrated no serious adverse events in well over 30,000 recorded exercise hours;¹⁰ 4) securing participants during all treadmill walking using a harness connected to an overhead support system for safety in case of loss of balance; 5) using appropriate guarding during overground walking and balance testing, which will be performed by physical therapists and physical therapist assistants; 6) instructing participants to stay hydrated and to eat within 3 hours prior to arriving for each exercise testing or training session; 7) providing water or a snack if the participant reports insufficient intake; 8) asking participants with insulin-dependent diabetes to take a blood glucose reading prior to exercise using their own testing supplies, providing a snack if blood glucose is low, and postponing study activities if blood glucose remains out of range (generally <95 or >250 mg/dL); and 9) ensuring that personnel performing finger stick blood sampling for lactate testing are trained in antiseptic technique and only collect the minimal needed amount of blood (approximately one drop).

We have completed 4 IRB-approved studies to date involving similar or identical screening, testing and training procedures, involving a total of over 50 participants. These studies have included extensive monitoring for adverse events (AEs), including participant interviews before and after each session and continuous observation of participants and electrocardiograms throughout each session. No serious AEs related to locomotor HIT have occurred. Normal exercise-related soreness and fatigue are the most commonly reported AEs, especially after the initial training sessions. These symptoms do not typically interfere with normal functioning or last longer than a day. In our pilot RCT, AE rates were similar between HIT and MAT (Table 7).⁹

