Table 7. Adverse Events (AEs) in Pilot RCT

Data reported as no. of participants with AE (total no. of AEs) [AE incidence rate per 100 sessions]

	HIT (n=13, sessions=141)	MAT (n=5, sessions=60)	HIT/MAT AE odds ratio (95% CI)
Any AE	9 (21) [14.9]	4 (8) [13.3]	1.14 (0.47-2.73)
Related to intervention	6 (13) [9.2]	1 (4) [6.7]	1.42 (0.44-4.55)
-Grade 1 (mild)	5 (10) [7.1]	1 (3) [5.0]	1.45 (0.38-5.47)
-Grade 2 (moderate)	2 (3) [2.1]	1 (1) [1.7]	1.28 (0.13-12.59)
-Grade 3-5 (severe-death)	0 (0) [0.0]	0 (0) [0.0]	N/A
-Cardiac disorder	0 (0) [0.0]	0 (0) [0.0]	N/A
-Joint/muscle pain	5 (8) [5.7]	1 (4) [6.7]	0.84 (0.24-2.91)
-Fatigue	3 (3) [2.1]	0 (0) [0.0]	3.03 (0.15-59.56)*
-Nausea	0 (0) [0.0]	0 (0) [0.0]	N/A
-Lightheadedness	1 (2) [1.4]	0 (0) [0.0]	2.15 (0.10-45.43)*
-Other nervous system	0 (0) [0.0]	0 (0) [0.0]	N/A
-Fall	0 (0) [0.0]	0 (0) [0.0]	N/A
-Other injury	0 (0) [0.0]	0 (0) [0.0]	N/A
Unrelated to intervention	6 (8) [5.7]	3 (4) [6.7]	0.84 (0.24-2.91)
-Grade 1 (mild)	5 (7) [5.0]	2 (2) [3.3]	1.51 (0.31-7.51)
-Grade 2 (moderate)	1 (1) [0.7]	2 (2) [3.3]	0.21 (0.02-2.33)
-Grade 3-5 (severe-death)	0 (0) [0.0]	0 (0) [0.0]	N/A
-Atrial fibrillation	1 (2) [1.4]	0 (0) [0.0]	2.15 (0.10-45.43)*
-Other cardiac disorder	0 (0) [0.0]	0 (0) [0.0]	N/A
-Joint/muscle pain	2 (2) [1.4]	1 (2) [3.3]	0.42 (0.06-3.03)
-Fatigue	1 (1) [0.7]	0 (0) [0.0]	1.28 (0.05-31.86)*
-Nausea	0 (0) [0.0]	0 (0) [0.0]	N/A
-Lightheadedness	1 (1) [0.7]	0 (0) [0.0]	1.28 (0.05-31.86)*
-Other nervous system	0 (0) [0.0]	0 (0) [0.0]	N/A
-Fall	1 (1) [0.7]	2 (2) [3.3]	0.21 (0.02-2.33)
-Other injury	1 (1) [0.7]	0 (0) [0.0]	1.28 (0.05-31.86)*

AE odds ratios are from logistic regression modeling of no. of AEs / no. of sessions per participant. CI, confidence interval. *Continuity corrected by adding 0.5 AEs to each group so that AE odds ratios could be calculated. HIT, high-intensity interval training; MAT, moderate-intensity aerobic training

Emergency Response Planning. Although we expect that the study will be safe, we are also well prepared for any unlikely events. AEs will be promptly reported to the IRB and DSMB (see Data and Safety Monitoring Plan above) and referrals for follow up care will be made according to the severity and type of event. Should an emergency medical situation occur during study activities, emergency medical care would be provided and the participant would be transported to the nearest emergency room.

G.2. Potential Benefits

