Hypothesis 2: To test the hypothesis that, compared with 4 and 8 weeks of HIT, 12 weeks of HIT will elicit significantly greater improvements in walking capacity and increased benefit over MAT, the same general linear model described above will be used. The hypothesis that 12 weeks of HIT will elicit greater improvements in primary and secondary outcomes compared to 4 and 8 weeks of HIT will be tested by the significance of the respective time contrasts within the HIT group. The hypothesis that HIT will elicit significantly greater improvements in primary and secondary outcomes from PRE to 8-WK and PRE to POST compared to MAT will be tested by the significance of the respective [group x time] contrasts. False discovery rate control will be applied for secondary outcomes.³

Prognostic Factor Testing

We will also test for baseline cofactors that may influence a stroke survivor's response to the interventions in this study. To do this, we will utilize a multivariate prognostic model that includes comfortable gait speed, lower extremity Fugl-Meyer motor scores, and scores on the Activities-Specific Balance Confidence Scale. These measures were selected based on previous studies suggesting that comfortable gait speed,⁴⁻⁹ lower limb Fugl-Meyer motor scores,⁹⁻¹¹ and balance abilities¹² may influence response to gait rehabilitation interventions in individuals with chronic stroke. Other potential cofactors will also be explored to inform future studies.

Safety Data Analysis

We expect a similar rate of non-serious adverse events (AEs) between HIT and MAT (e.g. temporary exercise-related soreness and fatigue), without any study-related serious AEs. In the unexpected event of one or more serious adverse events (SAE), the SAE rate will be compared between groups to confirm that there is no significant difference in major safety risk between HIT and MAT. A logistic regression model will be used for this analysis with SAE (yes/no) as the dependent variable and fixed effects for group, site, and baseline gait speed category. If there are SAE(s) in one group only, a continuity correction (0.5 SAEs added to each group) will still allow the odds ratio to be calculated.¹³

References

2. Dobkin BH. Progressive Staging of Pilot Studies to Improve Phase III Trials for Motor Interventions. *Neurorehabil Neural Repair*. 2009;23(3):197-206.

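### The adverse-events-per-session analysis names no allowance for clustering within participants; if events cluster, its standard errors will be too small

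*Protocol*

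**What the plan says.** The Protocol's Safety Data Analysis paragraph (E.2) first sets out a logistic model for SAEs, with one yes/no outcome per participant and fixed effects for group, site and baseline gait speed category. It then says that the secondary safety outcomes will be "tested using the same model, with [# AEs / # training sessions] as the dependent variable", and cites the pilot randomised trial (reference 9). No variance estimator or within-participant term is stated.

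The footnote to Table 7 (G.1) describes the pilot's method in the same way: "AE odds ratios are from logistic regression modeling of no. of AEs / no. of sessions per participant". The text that introduces Table 7 cites the same reference.

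The SAP's Safety Data Analysis section gives a model for SAEs only: "A logistic regression model will be used for this analysis with SAE (yes/no) as the dependent variable". It does not restate the AEs-per-session analysis.

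Two further statements bear on the point. On exposure: "Participants in both groups will be asked to perform 36 training sessions over approximately 12 weeks". On what counts as an AE: "This includes any adverse clinical change that occurs at any time following consent".

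**The concern.** Treating the SAE outcome as independent between participants is reasonable, because each person contributes one record. Carrying the same model over to AEs per session lets each person contribute up to 36 trials. An ordinary binomial likelihood then treats all sessions as exchangeable, given group, site and speed category.

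Repeat AEs in one person do no harm in themselves, since a binomial count already allows for them. The trouble arises only if some participants are more prone to AEs than chance variation and the three covariates explain. The point estimate is not the issue. The standard error would be too small, and a few participants with many AEs could look like a difference between HIT and MAT, with an interval that is too narrow.

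**Working it through.** **1. Which variance does the cited method use?** Table 7 gives 141 HIT sessions and 60 MAT sessions. With a and b the AE counts, treat sessions as independent trials:

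OR = a(60 − b) / [b(141 − a)]; SE(log OR) = √[1/a + 1/(141 − a) + 1/b + 1/(60 − b)].

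- Any AE (21 v 8): OR 1.14, SE 0.447, interval 0.47-2.73. Table 7 gives 1.14 (0.47-2.73).
- Related AEs (13 v 4): OR 1.42, SE 0.594, interval 0.44-4.55. Table 7 gives 1.42 (0.44-4.55).
- Related fatigue (3 v 0, with 0.5 AEs added per arm and sessions fixed): OR 3.03, interval 0.15-59.57. Table 7 gives 3.03 (0.15-59.56).

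All 16 estimable rows agree to within 0.01. The pilot intervals carry no allowance for clustering.

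**2. Does the pilot show clustering?** Table 7 gives participants affected and total AEs, so the possible splits can be bounded. Pearson dispersion is φ = Σ(y − mp)² / [mp(1 − p)] / df, taken within arm (12 df HIT, 4 df MAT). Assume equal sessions per participant.

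- Related, HIT (13 AEs in 6 of 13 people): m = 141/13, mp = 1.00, mp(1 − p) = 0.908. The most even split is 3,2,2,2,2,2 and seven zeros: (4 + 5 + 7)/0.908 = 17.6, and 17.6/12 = 1.47. For the most uneven split, the category rows (joint/muscle pain 8 AEs in 5 people, fatigue 3 in 3, lightheadedness 2 in 1) allow one person at most 4 + 1 + 2 = 7. That gives 7,2,1,1,1,1: (36 + 1 + 7)/0.908 = 48.5, and 48.5/12 = 4.04.
- Related, MAT (4 AEs, all in 1 of 5 people): mp = 0.8, mp(1 − p) = 0.747. (10.24 + 4 × 0.64)/0.747 = 17.1, and 17.1/4 = 4.29.
- Related, pooled: (17.6 + 17.1)/16 = 2.17 up to (48.5 + 17.1)/16 = 4.10.
- Any AE: in MAT, 1 person with related AEs and 3 with unrelated AEs make 4 affected, so nobody had both and the split must be 4,2,1,1,0 (φ = 1.66). In HIT, 6 + 6 − 9 = 3 people had both. The pooled range is 1.28-4.28.
- Unrelated, pooled: 1.00-1.21.

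The equal-sessions assumption matters. The pilot outcome table (Section C) has 11 HIT participants and Table 7 has 13, and 141 = 11 × 12 + 9. If 11 people had 12 sessions and two shared 9 (an assumption), the HIT minimum for related AEs falls to 1.21 and the pooled minimum to 1.98.

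**3. Size in the pilot.** Scaling the related-AE interval as 1.42 × exp(±1.96 × 0.594 × √φ) turns 0.44-4.55 into:

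- 0.40-5.1 at φ = 1.21
- 0.35-5.8 at φ = 1.47
- 0.26-7.9 at φ = 2.17

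These are illustrations from 17 events in 18 people.

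**4. Size in the planned trial.** The documents give no dispersion, so a range is assumed. If the true variance is φ times the binomial variance, the type I error of a nominal 5% test is 2[1 − Φ(1.96/√φ)]. With 36 sessions, φ = 1 + 35 × ICC, where ICC is the within-participant correlation. The simulations used about 50 participants and 36 sessions, with group, site and speed category in the model.

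| φ | implied ICC | formula | simulated, unscaled | simulated, dispersion-scaled |
|---|---|---|---|---|
| 1 | 0 | 5.0% | about 5% | about 5% |
| 1.5 | 0.014 | 11.0% | about 11% | about 5% |
| 2 | 0.029 | 16.6% | 17-19% | about 5% |
| 3 | 0.057 | 25.8% | 26-27% | about 5% |

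The inflation does not carry over to very rare categories. With about 5 events in the whole trial, and counting only simulated trials with events in both arms, the unscaled test rejected 0.2-3.2% of the time at φ from 1 to 2. At that event count, dispersion cannot be estimated usefully.

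**The case against.** The strongest reply is that silence is not a stated error. The Protocol describes the model in summary, the pilot report behind it is not available here, and the analyst may intend a scale option or random effect. This stands in part: the documents do not commit to independent sessions, and a reader who infers that they do goes too far. What they do show is a method with no clustering term, cited to a source whose intervals contain no such allowance.

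A reader might also infer that the pilot demonstrates clustering. It does not. The related-AE figure leans heavily on one MAT participant. HIT alone at its minimum of 1.47 is compatible with chance (p about 0.23 by simulation), and less striking still if sessions were unequal. Unrelated AEs show little or none. For any AE, Table 7 leaves a wide range.

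A third tempting reading is that the logistic form is itself wrong, because it allows at most one AE per session while AEs may occur at any time after consent. The mismatch is real but makes little difference: simulated error rates for the unscaled logistic test were 11.3%, 16.8% and 26.7% with capped counts, and 12.4%, 18.3% and 28.9% with uncapped counts, at dispersion 1.5, 2 and 3. A count model is an option, not a necessity.

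Finally, understated standard errors make a harm signal easier to flag, so a correction has a safety cost. That is fair and is counted below.

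**Conclusion.** The point holds conditionally. The plan names no allowance for within-participant clustering in the AEs-per-session analysis. If AEs cluster beyond binomial chance, intervals will be too narrow and false differences too frequent: roughly two to five times the nominal 5% at dispersions of 1.5 to 3. This rests on two things the documents do not settle: that plain binomial variance is intended, and that dispersion in this trial exceeds 1. The first is well supported by the Table 7 reproduction. The second is plausible for intervention-related AEs, but unknown.

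The severity is minor and the confidence moderate. These are secondary safety comparisons with no decision rule, and AEs also go to the IRB and the DSMB. The documents do not support a claim that the trial's safety assessment as a whole is unsound. The SAE analysis and the primary 6-minute walk analysis are unaffected.

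**What to change.** In the Protocol's Safety Data Analysis paragraph and the SAP's safety section, keep the logistic model and its fixed effects. Add that standard errors for the AEs-per-session analysis will be multiplied by the square root of the estimated Pearson dispersion, with the dispersion set to no less than 1 and a t reference distribution on the residual degrees of freedom. Two alternatives are acceptable: a small-sample-corrected robust variance clustered on participant, or an overdispersed count model with a log(sessions) offset. The latter reports a rate ratio where the pilot reported an odds ratio.

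Also state that the number of participants with at least one AE will be reported per arm for each grade and category, as in Table 7, and that this count will be relied on where events are too few to estimate dispersion.

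The cost is a sentence or two in each document and no new data. The downside is wider intervals, and somewhat less sensitivity to a harm signal, when AEs do cluster. When they do not, little is lost.
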